7.4.3 Method for Assigning Subject to Treatment Groups

Describe the randomization process and how the associated treatment assignment will be made.

Not applicable.

7.4.4 Subject Compliance Monitoring

Insert the procedures for monitoring subject compliance.

Not applicable.

7.4.5 Blinding of the Test Article

Describe how the test article is blinded.

Not applicable.

7.4.6 Receiving, Storage, Dispensing and Return

7.4.6.1 Receipt of Test Article

Describe how the test article will be obtained and from what source. Describe how the study test article will be packaged along with amounts (e.g., number of tablets/capsules or volume of liquid) and labeling. If drug kits are used, describe all the contents of the kit and associated labeling.

Investigative Substances: Microdialysis

The containers of the substances are dated upon receipt and when opened.

Research Agent	Source(s)
ACh	USP
L-NAME	EMD, Tocris
SNP	USP
Lactated Ringer's	McKesson, Owens and Minor

A license from the CRC physician, the nurse manager, or the overseeing physician is filed with vendors (e.g. VWR, McKesson, Moore Medical) requiring the documentation for the purchase of some investigative agents (e.g. Lactated Ringer's). The investigative agents are shipped to Noll Lab or picked up from the pharmacy by lab personnel. Copies of the prescriptions and orders are maintained in [name] laboratory files.

7.4.6.2 Storage

Describe the plans to store, handle the test article so they will be used only on subjects and only by authorized investigators. Describe storage temperature requirements and how temperature will be monitored and recorded.

Drugs used with microdialysis:

The room temperatures are recorded daily during weekdays. The temperature of the room is also monitored by the Central Control System of the Environmental Systems at PSU.

The drugs used with microdialysis in their solid form are stored under environmental conditions according to manufacturer's instructions in cabinets, refrigerators, or freezers located in room 224A or 228 Noll Laboratory. Opened drugs in their solid form are discarded after one year. The rooms are locked when unoccupied.

All of the chemicals are purchased in solid form and are stable for years when stored according to manufacturer's instructions. All of the chemicals are purchased in small vials that are exhausted within one to several weeks. Once mixed, stock solutions of substances are used within one week of stored in the refrigerator and within 6 months if stored in the freezer. Final dilutions of solutions that are prepared for an experiment are used within a couple of minutes to hours of preparation.

7.4.6.3

Preparation and Dispensing

Describe how the test article will be assigned to each subject and dispensed. Describe the steps necessary to prepare the test article. Include where the test article preparation will be done and by whom. Fully describe how the study treatment is to be administered and by whom.

None of the microdialysis drugs are dispensed to the subject; rather they are used in the experiments. All subjects will receive all test articles. A physician provides medical oversight for the preparation and administration of investigational agents via intradermal microdialysis (See Physician Oversight SOP).

Preparation of the Microdialysis Perfusates

Test article preparation will occur in Noll Lab.

When mixing the perfusates, the lab personnel performing microdialysis washes their hands, wears protection (e.g. gloves, lab coat), and uses glassware that has been washed with cleanser (Alconox, designed for use with healthcare instruments, pharmaceutical process equipment, tissue culture apparatus, etc.), and rinsed multiple times in tap water and then doubly-distilled water and air-dried. The solid investigational agents are weighed on a microbalance and then mixed with sterile pharmaceutical-grade lactated Ringer's solution to the desired concentration (See **Treatment Regimen**). The solution is drawn into a syringe through a 0.2 μ m filter. Prior to injecting a solution into or withdrawing a solution from a sterile container through a sterile hypodermic needle, the stopper of the sterile container is cleaned thoroughly with alcohol. The final dilutions of the perfusates are drawn into sterile syringes through 0.2 μ m filters within minutes or hours of their use in the experiment.

The lab personnel performing microdialysis will use the study treatments in the microdialysis experiments.

7.4.6.4

Return or Destruction of the Test Article

Describe the procedures for final reconciliation of the test article supply at the end of the study and whether the test article is to be shipped back to a source or destroyed on site.

Investigative substances are usually consumed in the experiments. Investigative substances not consumed by the experiments are disposed of in accordance with the policies of Environmental Health and Safety of Penn State. Some substances (e.g. protein or peptide-based) are autoclaved prior to disposal.

7.4.6.5

Prior and Concomitant Therapy

Describe what prior and/or concomitant medical therapy will be collected. Describe which concomitant medicines/therapies are permitted during the study. Describe which concomitant medicines are not permitted during the study.

Not applicable.

8.0 Subject Numbers and Statistical Plan

8.1 Number of Subjects

Indicate the total number of subjects to be accrued.

If applicable, distinguish between the number of subjects who are expected to be enrolled and screened, and the number of subjects needed to complete the research procedures (i.e., numbers of subjects excluding screen failures.)

For the main study, a total of 30 survivors of either leukemia/lymphoma or breast cancer will be enrolled. The ancillary lab study will enroll 10 breast cancer survivors from the main study (i.e., from the 30 participants already enrolled).

8.2 Sample size determination

If applicable, provide a justification of the sample size outlined in section 8.1 – to include reflections on, or calculations of, the power of the study.

Assuming a 5% type-1 error rate, this sample size affords 80% power for detecting pre-post changes in the primary outcome of $d=0.47$ (one tailed)/ $d=0.53$ (two-tailed). Effect sizes for secondary outcomes will be used to inform planning for a future clinical trial.

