1.2 Primary Study Endpoints

State the primary endpoints to be measured in the study. Clinical trials typically have a primary objective or endpoint. Additional objectives and endpoints are secondary. The endpoints (or outcomes), determined for each study subject, are the quantitative measurements required by the objectives. Measuring the selected endpoints is the goal of a trial (examples: response rate and survival).

Change in total physical activity volume from baseline to 3 and 6 month as measured by the Actigraph GT3XP-BTLE (total activity counts).

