7.0 Study Design and Procedures

7.1 Study Design

Describe the type/design of trial to be conducted (e.g., double-blind, placebo controlled, parallel design, etc.). Provide a schematic diagram of study design, procedures and stages, if appropriate.

We propose a single-group pre-post behavioral intervention trial (N=30) with an ancillary lab study on a sub-sample (n=10) to gather mechanistic data on changes in microvascular function.

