8.3 Statistical methods

Describe the statistical methods (or non-statistical methods of analysis) that will be employed.

Descriptive statistics will be calculated for all variables. Paired-samples t-tests (under intent to treat principles) will be used to test for differences from baseline-3 mos and 3-6 mos in motivation and physical activity (Aim 1) and fitness and vascular function (Aim 2). Given the lack of a control group, effect sizes (standardized mean differences) will be emphasized when interpreting data. Sensitivity analyses will be conducted using patients with/without radiation therapy.

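### The 5% error rate and 80% power in section 8.2 hold for one contrast, but the plan has two primary time points and two tests, with no rule for which decides

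*Combined protocol and SAP*

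**What the plan says.** - **Section 1.2 (primary endpoint).** One measure, Actigraph total activity counts, at two time points: "Change in total physical activity volume from baseline to 3 and 6 month".
- **Section 8.2 (sample size).** One error rate and one power: "Assuming a 5% type-1 error rate, this sample size affords 80% power for detecting pre-post changes in the primary outcome". The detectable effect is given twice, as d=0.47 one-tailed and d=0.53 two-tailed. No contrast is named.
- **Section 8.3 (methods).** Paired t-tests "will be used to test for differences from baseline-3 mos and 3-6 mos in motivation and physical activity (Aim 1", with fitness and vascular function under Aim 2. The section states no alpha, testing order, adjustment or success rule. It also says that effect sizes will carry the interpretation because there is no control group.
- **Sections 7.1 and 8.1.** "We propose a single-group pre-post behavioral intervention trial (N=30"; "a total of 30 survivors of either leukemia/lymphoma or breast cancer will be enrolled".
- **Sections 7.2.3 and 7.2.4.** The app is used for the first three months and removed at the month 3 visit, so the 3-to-6-month interval is off-app.

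**The concern.** An error rate and a power belong to a defined test or a defined decision rule. Here the primary endpoint offers two changes, the methods section tests two contrasts, and the sample size section supplies one pair of figures without attaching it to any of them. The two sections also differ on the later contrast: 1.2 implies baseline to 6 months, while 8.3 tests 3 to 6 months.

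Without a stated rule, the choice of deciding contrast can be made after the data are seen. A positive result on either one could then be reported as a positive primary result at a nominal 5%, although the chance of such a result under no change would be higher. The figures used to justify N=30 would not describe that decision.

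**Working it through.** **Inputs.** From the documents: N=30 in a single group (7.1, 8.1); 5% and 80%, d=0.47 one-sided or d=0.53 two-sided (8.2); paired t-test (8.3). Assumed: the correlation r between the two change scores, which is not in the documents and is varied from -0.9 to +0.9.

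**Step 1: reproduce the plan's figure.** For a paired t-test the degrees of freedom are 30 - 1 = 29 and the noncentrality is d × √30. Power is the probability that a noncentral t exceeds the critical value (in either tail if two-sided).

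| Test | Critical t | Noncentrality | Power |
|---|---|---|---|
| Two-sided 5%, d=0.53 | 2.045 | 0.53 × 5.477 = 2.903 | 80.1% |
| One-sided 5%, d=0.47 | 1.699 | 0.47 × 5.477 = 2.574 | 80.75% |

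Solving for exactly 80% gives d=0.529 and d=0.465. The figures in 8.2 are therefore correct for one contrast tested at an unadjusted 5%.

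**Step 2: two tests, either one sufficient.** If the tests were independent, the chance of at least one false positive would be 1 - 0.95² = 9.75%. With correlated changes it was simulated (two paired t-tests, N=30, 100,000 trials per setting, no true change):

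| r | Two-sided 5% each | One-sided 5% each |
|---|---|---|
| -0.9 | 7.0% | 9.9% |
| -0.5 | 9.1% | 10.0% |
| 0 | 9.8% | 9.8% |
| +0.5 | 9.3% | 8.8% |
| +0.9 | 7.2% | 6.7% |

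Two of these rows are natural reference points. Suppose the three visits have equal variance σ² and equal pairwise correlation ρ. Each change then has variance 2σ²(1 - ρ). The covariance of the baseline-3 and baseline-6 changes is σ²(1 - ρ), so r = +0.5. The covariance of the baseline-3 and 3-6 changes is -σ²(1 - ρ), so r = -0.5. Under that structure the two-sided error is 9.3% for the pair in 1.2 and 9.1% for the pair in 8.3, whatever ρ is.

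**Step 3: keep 5% by splitting it.** At 2.5% per contrast (Bonferroni), N=30:

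| Test | Critical t | Power per contrast | d at 80% power | N for 80% at the stated d |
|---|---|---|---|---|
| Two-sided, d=0.53 | 2.364 | 70.4% | 0.59 | 37 |
| One-sided, d=0.47 | 2.045 | 70.1% | 0.53 | 38 |

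**Step 4: keep 5% by ordering.** If one contrast is tested first at the full 5% and the second only after the first is significant, the family-wise error stays at 5%. The first contrast keeps the power in Step 1 (80.1% or 80.75%) with N=30.

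**The case against.** The strongest reply is that 8.2 is not wrong. It does not claim control across several tests, its figures reproduce, and a design described as pre-post with a three-month app period suggests baseline to 3 months as the intended contrast. On that reading both the 5% and the 80% stand. This is fair as far as it goes: the figures are incomplete rather than false. But 1.2 gives the 6-month change equal primary status, and no section states the narrower reading.

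A second reply is that 8.3 gives no alpha, so testing each contrast at a full 5% is an inference. That also stands. The inference has some support, since the 80% is reached only with an unsplit 5%, but the 7-10% must be stated as conditional on it.

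A third reply is that interpretation will rest on effect sizes and that an uncontrolled study of 30 has larger limitations than this one. That lowers the severity. It does not remove the point, because 8.3 still plans tests and 8.2 still justifies N by error rate and power for the primary outcome.

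A reader might go further and infer that the design must lose either its 5% or its 80%, with power of only 61-70%. The documents do not support this. The choice is not forced: a single named contrast or a fixed order keeps both figures. The 61-70% is joint power when both contrasts must be significant, for r from -0.5 to +0.5, with the stated d holding in each. No section requires both to be positive. For the pair in 8.3 it would also need a second gain of d=0.53 (two-sided) or d=0.47 (one-sided) after the app is removed, which no section predicts.

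**Conclusion.** The point holds as a gap in the decision rule for the primary endpoint. The 5% and 80% in 8.2 describe one contrast, the plan carries two, and nothing says which decides or how the error rate is kept.

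If either contrast may support the claim at two-sided 5% each, the chance of at least one false positive is about 7-10% instead of 5%. The one-sided option in 8.2 gives much the same range. Both rest on the either-may-count rule, on unadjusted testing and on the assumed correlations. If alpha were split instead, power would be about 70% per contrast at the effects stated in 8.2.

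Severity is moderate. The gap concerns the primary endpoint and should be closed before analysis, but this is a single-group pilot in which effect sizes are to be emphasised.

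**What to change.** 1. In 1.2, 8.2 and 8.3, name the change in Actigraph counts from baseline to 3 months (the on-app period) as the primary contrast, to which the 5% and 80% apply.
2. In 8.2, choose one sidedness and quote only the matching effect size.
3. Reconcile 1.2 with 8.3 by making the baseline-to-6-month change the second contrast, tested at 5% only if the first is significant (fixed sequence).
4. Report the 3-to-6-month change as an estimate with a 95% CI.

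The tests planned for secondary outcomes need not change on account of this point.

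The cost is a few sentences in three sections. No participants are added, alpha is not divided, and power for the first contrast stays at 80%. The downside is that a formal 6-month claim depends on the 3-month result: if the first test is not significant, the 6-month change can be reported only as an estimate.

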3.3 Early Withdrawal of Subjects

3.3.1 Criteria for removal from study

Insert subject withdrawal criteria (e.g., safety reasons, failure of subject to adhere to protocol requirements, subject consent withdrawal, disease progression, etc.).

Research is optional, and participants have the right to withdraw their consent at any time throughout the study. When withdrawing from the study, the participant should let the research team know that he/she wishes to withdraw. Participants may provide the research team with the reason(s) for leaving the study but are not required to provide their reason. Refusal to take part in or withdraw from this study will involve no penalty or loss of benefits one would receive otherwise.

If participants have a recurrence of cancer during the study period and initiate a new round of treatment they will be removed from the study, consistent with the study's exclusion criteria.

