7.2.5 Lab Visit 3 (Month 6)

Participants will then be asked to come back into the lab one final time approximately 6 months following their initial baseline visit. All measures taken at baseline and 3 months will again be taken at 6 months.

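### The 80% power in Section 8.2 needs all 30 enrolled to give complete pairs, with no allowance for loss, and Section 8.3 omits the baseline-to-6-month contrast of the primary endpoint

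*Combined protocol and SAP*

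**What the plan says.** Section 8.1 says that "a total of 30 survivors of either leukemia/lymphoma or breast cancer will be enrolled". It gives no separate number of participants needed to complete. Section 8.2 sets a 5% type 1 error rate and says that "this sample size affords 80% power for detecting pre-post changes in the primary outcome of $d=0.47$ (one tailed)/ $d=0.53$ (two-tailed", without mentioning loss.

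Section 3.3.1 foresees two routes of loss: "participants have the right to withdraw their consent at any time throughout the study", and those whose cancer recurs and who "initiate a new round of treatment they will be removed from the study". Section 3.3.2, on follow-up of withdrawn subjects, is answered as not applicable. Under Section 7.2.4 the month-3 accelerometer, which carries the primary outcome, is worn for a week and posted back.

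Section 1.2 defines the primary endpoint as "Change in total physical activity volume from baseline to 3 and 6 month". Section 7.2.5 confirms that "All measures taken at baseline and 3 months will again be taken at 6 months". Section 8.3 then says: "Paired-samples t-tests (under intent to treat principles) will be used to test for differences from baseline-3 mos and 3-6 mos". It also says that "effect sizes (standardized mean differences) will be emphasized when interpreting data". It gives no rule for a missing visit. Its only sensitivity analysis concerns radiation therapy.

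**The concern.** A paired t-test uses only people with both measurements, so the n behind a power figure for it is a number of complete pairs. Here that number equals the number enrolled. A reader will take 80% as the power of a trial that enrols 30, when it is the power of one that also loses nobody.

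Two gaps in Section 8.3 add to this. The intent-to-treat label implies that everyone enrolled is analysed, but the named test cannot do that once a visit is missing unless values are imputed, and imputation is not mentioned. Two analysts could follow the section faithfully and report different samples. The second gap exists even with no loss: no listed test addresses change from baseline to 6 months, which is half of the stated primary endpoint.

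**Working it through.** **Step 1: reproduce the plan's figure.** Inputs: n=30 (8.1), alpha 5% and d=0.47 one-tailed or 0.53 two-tailed (8.2), paired t-test (8.3). Power is the probability that a noncentral t variable with n−1 degrees of freedom and noncentrality d√n exceeds the critical value (plus the negligible lower tail when two-sided).

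- Two-sided: 0.53 × √30 = 2.90, critical t(29) = 2.045, power 80.1%.
- One-tailed: 0.47 × √30 = 2.57, critical t(29) = 1.699, power 80.7%.

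The effects detectable with 80% power are 0.529 and 0.465, consistent with the stated 0.53 and 0.47. The plan's figure is reproduced, and 30 is the smallest n reaching 80% for both.

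**Step 2: allow for missing pairs.** The documents give no loss rate, so 10% to 30% is an assumed range. Pairs = 30 × (1 − loss), with only complete pairs analysed.

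| Pairs | Loss | Two-sided power, d=0.53 | One-tailed power, d=0.47 | Detectable d, two-sided / one-tailed | Two-sided power, d=0.75 |
|---|---|---|---|---|---|
| 30 | none | 80.1% | 80.7% | 0.53 / 0.47 | 97.8% |
| 29 | one pair | 78.7% | 79.5% | 0.54 / 0.47 | 97.4% |
| 27 | 10% | 75.5% | 76.8% | 0.56 / 0.49 | 96.3% |
| 24 | 20% | 70.1% | 72.2% | 0.60 / 0.52 | 94.0% |
| 21 | 30% | 63.7% | 66.8% | 0.64 / 0.56 | 90.5% |

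The last column uses the preliminary effect on total activity volume in Section 2.2. These figures are for baseline to 3 months. None is given for 3 to 6 months, an interval that starts when the app is removed (7.2.4).

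**Step 3: compare endpoint and tests.** Section 1.2 asks for change from baseline to 3 months and to 6 months. Section 8.3 lists baseline to 3 and 3 to 6. With complete data the two mean changes add up to the baseline-to-6 change, but its standard error and test do not follow from the two listed tests. With incomplete data, the two tests may also rest on different people.

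**Step 4: would a model using all available visits help?** The model considered is a repeated-measures mixed model (categorical visit, unstructured covariance, Kenward-Roger degrees of freedom).

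- *Complete data.* It gives the same t statistics as the paired tests; in a check with n=30 both gave 2.825, −0.971 and 1.645 for the three contrasts.
- *Power.* Simulation used 6,000 trials per cell, assumed between-visit correlations of 0.5 to 0.85, and month 3 missing completely at random. Two-sided power for baseline to 3 months was 74.8–78.5%, 71.2–74.2% and 63.8–67.6% at 10%, 20% and 30% loss. That is 0 to 4 points above the paired test on the same data.
- *Bias, loss depending on baseline activity.* The complete-pair bias in d is −√((1−r)/2) × the mean baseline z-score of those retained. At an assumed 20% loss, with odds of loss 1.65 to 2.72 times higher per SD lower baseline, that mean is 0.096 to 0.173. The bias runs from −√0.075 × 0.096 = −0.026 (r=0.85) to −√0.25 × 0.173 = −0.087 (r=0.5). A true 0.53 is then estimated as 0.44–0.50 by complete pairs and about 0.53 by the model.
- *Bias, loss depending on month-3 activity.* With the same loss rate, slopes and correlations, complete pairs give 0.56–0.62 and a likelihood estimate using baseline gives 0.58–0.66, further from 0.53.

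**The case against.** The strongest reply is that intent to treat normally means that everyone enrolled is analysed, so 30 is the analysed number and nothing in Section 8.2 is overstated. Loss may also be low. Participants complete a wear-and-return week before enrolment (7.2.1), so their baseline accelerometer data appear to be in hand already and only the follow-up measurement is at risk. The app runs by itself (7.2.3), visits are paid (14.0), and compliance calls are mentioned (9.1.1.1). This is a single-group study of 30 that emphasises effect sizes, and at d=0.75 power is ample even with 30% loss.

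Much of this stands. The shortfall is conditional on an assumed loss rate and on complete-case analysis, and Section 8.3 does not actually commit to complete-case analysis. Three things do not fall away:

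- The label does not supply the missing values, and no method for doing so is named.
- The d=0.75 came from healthy adults over 8 weeks, and the plan chose to state its power at 0.47 and 0.53.
- Reliance on effect sizes makes selective loss more relevant, because it can shift the estimate whatever the power.

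None of these replies touches the missing baseline-to-6 contrast.

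A reader might also infer that a mixed model would cure the bias. The documents do not support that. It helps if loss depends on observed values. But recurrence with new treatment, the removal cause that Section 3.3.1 names, arises after baseline and could be tied to unobserved follow-up activity. In that case the model can do worse than complete pairs.

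**Conclusion.** The point holds in a limited form. The 80% is correct for 30 complete pairs and has no reserve, since one lost pair takes both versions just below 80%. Assuming 10% to 20% loss and complete-pair analysis, two-sided power at d=0.53 is 75.5% to 70.1%, and one-tailed power at d=0.47 is 76.8% to 72.2%. That is modest at the low end, and at d=0.75 two-sided power remains at 94% or more over the same range.

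A reader might go further and conclude that Section 8.2 is miscalculated or that the trial is underpowered. Neither follows: the calculation reproduces, no loss rate is given, and the true effect is unknown.

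The omission of baseline to 6 months is a separate mismatch between Sections 1.2 and 8.3. It needs no assumption about loss.

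**What to change.** 1. **Section 8.2.** Restate the figure as the baseline-to-3-month power of the paired t-test with 30 complete pairs. Add that the detectable d becomes 0.49–0.52 (one-tailed) or 0.56–0.60 (two-tailed) if 10%–20% of pairs are missing.
2. **Section 8.3, contrasts.** Add baseline to 6 months for the primary outcome.
3. **Section 8.3, missing visits.** Choose one of two routes. Either label the paired t-tests complete-case, drop or define the intent-to-treat wording, and report the number of pairs per contrast. Or keep the wording and analyse all available visits of everyone enrolled with a repeated-measures mixed model, with complete-pair t-tests as sensitivity. On the second route report both results, because which is less biased depends on why visits are missing.

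The cost is wording in two sections, a less favourable stated power and a little more analysis. The model relies on missing-at-random and recovers only about 0 to 4 points of power. No extra enrolment is needed. Keeping 30 pairs by over-enrolment would instead take 30/0.9, or 34 participants, at 10% loss and 30/0.8, or 38, at 20%.
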